6.2.2.2 Up-titration phase

Patients will have weekly contact to the study site during the up-titration phase either as office visits or telephone calls. The complete seven weeks of up-titration are used to safely increase the study medications to the highest tolerated optimal dose for effective response. The investigator should use his/her clinical judgment in adjusting the dose to a dose where clinical improvement is reached. Furthermore, if a patient is unable to tolerate an increased dose level, the medication can be lowered one level.

It is possible that the L-Dopa⁺ dose may need to be adjusted with the addition of Pramipexole (SR or IR) during the up-titration Phase.

Visit 3 (i.e., week 2) at day 14 ± 2:

- Obtain vital signs (blood pressure, pulse) and weight
 - Check for abnormal behavior. The MMIDI sub-scale has to be completed if the patient experiences any abnormal behavior
 - Ask patient to score the severity of EMO
 - Ask patient to complete the ESS
 - Ask patient to complete the PDSS-2
 - Ask patient to complete the NHQ Section 1. NHQ Section 2 should be completed by spouses or caregivers who are with the patients during the night at the same day. If no spouses or caregivers during the night, document it in the medical note and no need to complete NHQ Section 2.
 - Ask patient to complete the SCOPA-Sleep
 - Ask patient to complete the PGI-I questionnaire
 - Perform medication compliance check
 - Review concomitant therapies including PD therapies
 - Record AEs or follow-up on AEs continuing from a prior visit
 - Dispense study medication to the patient to ensure the sufficient study medication until the next on-site visit with verbal instructions on how to take the medication. Remind the patient to take the study medication Pramipexole IR regularly three times per day with the third dose at 7-9 pm before bedtime or take study medication Pramipexole SR once daily at 7- 9 pm before bedtime. Additionally, remind the patient to bring the medication boxes (including all blank blister(s), unused and partially used study medication) back at the next scheduled on-site visit. The unused and partially used study medication will be returned to patients for treatment after drug accountability until the end of treatment.
-
- Schedule patient's next contact (telephone call, TC2) to study site one week later

Visit 4 (i.e., week 4) at day 28 ± 2:

- Obtain vital signs (blood pressure, pulse) and weight

- Check for abnormal behavior. The MMIDI sub-scale has to be completed if the patient experiences any abnormal behavior.
- Perform MDS-UPDRS part IV
- Perform CGI-I questionnaire
- Ask patient to score MDS-UPDRS part II
- Ask patient to score the severity of EMO
- Ask patient to complete the PGI-I questionnaire
- Ask patient to complete the ESS
- Ask patient to complete the PDSS-2
- Ask patient to complete the NHQ Section 1. NHQ Section 2 should be completed by spouses or caregivers who are with the patients during the night at the same day. If no spouses or caregivers during the night, document it in the medical note and no need to complete NHQ Section 2.
- Ask patient to complete the SCOPA-Sleep
- Perform medication compliance check
- Review concomitant therapies including PD therapies
- Record AEs or follow-up on AEs continuing from a prior visit
- Dispense study medication to ensure the sufficient study medication until the next on-site visit the patient with verbal instructions on how to take the medication. Remind the patient to take the study medication Pramipexole IR regularly three times per day with the third dose at 7-9 pm before bedtime or take study medication Pramipexole SR once daily at 7- 9 pm before bedtime.. Additionally, remind the patient to bring the medication boxes (including all blank blister(s), unused and partially used study medication) back at the next scheduled on-site visit. The unused and partially used study medication will be returned to patients for treatment after drug accountability until the end of treatment.
- Review the health economics questionnaire. Instruct and supply one with patient to bring home.
- Ask a patient's caregiver to complete CBI at on-site visit. If the caregiver absent on-site visit, patients should bring this questionnaire to her/his caregiver to complete it at the same day. If no caregiver, document it in the medical note and no need to complete CBI.
- Schedule patient's next contact (telephone call, TC3) to study site one week later
- Schedule patient's under next contact (telephone call, TC4) to study site two weeks later
- Schedule patient's fifth contact (telephone call, TC5) to study site three weeks later

Interim Telephone Calls (TC1 to TC5):

Interim telephone calls will be performed in order to avoid weekly on-site visits for the patients. If for some instance a patient will not have telephone access at home, the patient could perform a clinic visit. These unscheduled visits need to be reported then formally as TC's with a remark in the comments section of the corresponding eCRF page.

In the telephone calls the following information needs to be obtained:

- Check medication compliance
- Ask patient to complete the PGI-I questionnaire (the value will be recorded in the eCRF)
- Review concomitant therapies including PD therapies
- Record AEs or follow-up on AEs continuing from a prior visit. Evaluate patient's response to current dose level. If warranted, increase to next dose level. If patient is

already at optimal dose level, instruct patient to continue with the same dose level. If patient experienced side effects, the dose level can be adjusted to the next lower dose level.

- Schedule patient's next on-site visit.

TC5 will be the last time when the investigator can decide to down-titrate or to up-titrate the study medication. From TC3 to TC5, if pramipexole dose should be adjusted due to unsatisfactory efficacy or adverse event, on-site visit should be added to adjust dose.

6.2.2.3 Maintenance phase

In this phase three on-site visits will be performed (V5 to V7). During the maintenance phase, no dose adjustments will be allowed for the study medication. A patient's dose will be adjusted for medical reasons if considered in the best interest of the patient upon agreement between investigators and Sponsor.

Visit 5 - week 8, day 56 ± 3:

- Obtain vital signs (blood pressure, pulse) and weight
- Perform CGI-I questionnaire
- Ask patient to score the severity of EMO
- Ask patient to complete the PGI-I questionnaire
- Ask patient to complete the ESS
- Ask patient to complete the PDSS-2
- Ask patient to complete the NHQ Section 1. NHQ Section 2 should be completed by spouses or caregivers who are with the patients during the night at the same day. If no spouses or caregivers during the night, document it in the medical note and no need to complete NHQ Section 2.
- Ask patient to complete the SCOPA-Sleep
- Ask patient to complete the quality of life assessment (PDQ-8 and EQ-5D-5L)
- Perform medication compliance check
- Review concomitant therapies including PD therapies
- Record AEs or follow-up on AEs continuing from a prior visit
- Dispense study medication to the patient to ensure the sufficient study medication until the next on-site visit with verbal instructions on how to take the medication. Remind the patient to take the study medication Pramipexole IR regularly three times per day with the third dose at 7-9 pm before bedtime or take study medication Pramipexole SR once daily at 7- 9 pm before bedtime. Additionally, remind the patient to bring the medication boxes (including all blank blister(s), unused and partially used study medication) back at the next scheduled on-site visit. The unused and partially used study medication will be returned to patients for treatment after drug accountability until the end of treatment.

- Schedule patient's next visit (Visit 6) four weeks later

Visit 6 - week 12, day 84 ± 3:

- Obtain vital signs (blood pressure, pulse) and weight
- Check for abnormal behavior. The MMIDI sub-scale has to be completed if the patient experiences any abnormal behavior.
- Ask patient to score the severity of EMO
- Ask the patient to complete the PGI-I questionnaire
- Ask patient to complete the ESS questionnaire
- Ask patient to complete the PDSS-2
- Ask patient to complete the NHQ Section 1. NHQ Section 2 should be completed by spouses or caregivers who are with the patients during the night at the same day. If no spouses or caregivers during the night, document it in the medical note and no need to complete NHQ Section 2.
- Ask patient to complete the SCOPA-Sleep
- Perform medication compliance check
- Review concomitant therapies including PD therapies
- Record AEs or follow-up on AEs continuing from a prior visit
- Dispense study medication to the patient to ensure the sufficient study medication until the next on-site visit with verbal instructions on how to take the medication. Remind the patient to take the study medication Pramipexole IR regularly three times per day with the third dose at 7-9 pm before bedtime or take study medication Pramipexole SR once daily at 7- 9 pm before bedtime. Additionally, remind the patient to bring the medication boxes (including all blank blister(s), unused and partially used study medication) back at the next scheduled on-site visit. The unused and partially used study medication will be returned to patients for treatment after drug accountability until the end of treatment.

- Schedule patient's next visit (Visit 7) six weeks later

Visit 7 - week 18, day 126 ± 3 or premature discontinuation:

All patients should complete these assessments, even those who terminate early.

- Obtain vital signs (blood pressure, pulse) and weight
- Perform comprehensive physical examination (including heart, lungs, abdomen, extremities, height and weight, etc.) including also a skin examination

- Perform CGI-I questionnaire
- Perform MMIDI

- Ask patient to score the severity of EMO
- Ask the patient to complete the PGI-I questionnaire
- Ask patient to complete the ESS questionnaire
- Ask patient to complete the PDSS-2
- Ask patient to complete the NHQ Section 1. NHQ Section 2 should be completed by spouses or caregivers who are with the patients during the night at the same day. If no spouses or caregivers during the night, document it in the medical note and no need to complete NHQ Section 2.
- Ask patient to complete the SCOPA-Sleep
- Ask patient to complete the quality of life assessment (PDQ-8 and EQ-5D-5L)

- Collect fasted blood sample for safety laboratory evaluation
- Perform spot urine pregnancy test (for females with childbearing potential)
- Perform medication compliance check
- Review concomitant therapies including PD therapies
- Record AEs or follow-up on AEs continuing from a prior visit
- Perform a 12-lead ECG
- Dispense study medication to ensure the sufficient study medication for the down-titration phase if patient won't continue Pramipexole IR/SR treatment after trial completion. Remind those patients to take the study medication Pramipexole IR regularly three times per day with the third dose at 7-9 pm before bedtime or take study medication Pramipexole SR once daily at 7- 9 pm before bedtime. Additionally, remind the patient to bring the medication boxes (including all blank blister(s), unused and partially used study medication) back at the next scheduled on-site visit.
Return the study medication boxes (including all blank blister(s), unused and partially used study medication) to study site if patient will continue Pramipexole IR/SR treatment after trial completion at this visit.

- Schedule patient's next visit (Visit 8) one week later.

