Week(s)	-2 to -1	0	1	2	3	4	5	6	7	8	12	18	Not applicable
Day(s)	-14 to -3	0	7	14	21	28	35	42	49	56	84	126	Last study dose +2
Time window for visits Day(s)	0	0	±2	±2	±2	±2	±2	±2	±2	±3	±3	±3	+3
Written Informed consent ³	x												
Assign patient number	x												
Supply Trial identification card	x												
Demographics	x												
Medical history	x												
Review of In-/exclusion criteria	x	x											
Physical examination	x											x	
BP, Pulse, Weight, Height ⁴	x	x		x		x				x	x	x	x
Check for abnormal behavior ⁷				x		x					x		
MMIDI		x								x		x	x
MMSE	x												
Modified Hoehn and Yahr stage at on-time	x												
Randomization		x											
Instruct and supply patient diary	x												
Review patient diary		x											
EMO		x		x		x				x	x	x	

Proprietary confidential information © 2018 Boehringer Ingelheim International GmbH or one or more of its affiliated companies

Trial Period	S ¹	R ¹	Flexible up-titration phase							Maintenance phase			Follow up visit after <down titration phase/EOT>
Visit	V1	V2	TC1	V3	TC2	V4	TC3 ¹¹	TC4 ¹¹	TC5 ¹¹	V5	V6	V7 ²	V8 ²
Weeks	-2 to -1	0	1	2	3	4	5	6	7	8	12	18	Not applicable
Days	-14 to -3	0	7	14	21	28	35	42	49	56	84	126	Last study dose +2
Time window for visits Day(s)	0	0	±2	±2	±2	±2	±2	±2	±2	±3	±3	±3	+3
CGI-I						×				×		×	
PGI-I			×	×	×	×	×	×	×	×	×	×	
ESS		×		×		×				×	×	×	
PDSS-2		×		×		×				×	×	×	
NHQ		×		×		×				×	×	×	
SCOPA-Sleep		×		×		×				×	×	×	
PDQ-8		×								×		×	
Safety lab tests	×											×	×
Urine Pregnancy test ⁹ (if applicable)	×											×	
12-lead ECG	×											×	×
Dispense trial drugs		×		×		×				×	×	×	
Compliance check			×	×	×	×	×	×	×	×	×	×	×
Concomitant therapy	×	×	×	×	×	×	×	×	×	×	×	×	×
Adverse events	×	×	×	×	×	×	×	×	×	×	×	×	×
Instruct and supply health economics questionnaire	×	×		×		×				×	×		
Review health economics questionnaire ¹⁰		×		×		×				×	×	×	

1. Abbreviations are for “Screening” and “Randomization”.
 2. All assessments planned at visit 7 and visit 8 have to be done even if a patient is prematurely withdrawn from the treatment phase. For visit 8, follow up visit after down-titration phase or follow up visit after EOT (end of treatment) should be conducted after the end of residual effect period (i.e., 2 days after the last study dose)
 3. Re-consenting may become necessary when new relevant information becomes available and should be conducted according to the sponsor’s instructions.
 4. Height will only be measured at Screening (visit 1).

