4.1.2 Selection of doses in the trial

The dosing schedule for this study follows the standard doses for Pramipexole. Doses for this study used during the up-titration and the maintenance phase consist of the following seven dose levels:

Pramipexole SR 0.375 mg, 0.75 mg, 1.5 mg (0.75 mg*2), 2.25 mg (0.75 mg*3), 3.0 mg (0.75 mg *4), 3.75 mg (0.75 mg*5) or 4.5 mg (0.75 mg*6) at 7-9 pm before bedtime.

Pramipexole IR 0.375 mg (0.25mg*1/2 t.i.d.), 0.75 mg (0.25 mg t.i.d.), 1.5 mg (1.0mg*1/2 t.i.d.), 2.25 mg (1.0 mg *1/2 t.i.d. +1.0 mg *1/4mg t.i.d.), 3.0 mg (1.0 mg t.i.d.), 3.75 mg (1.0 mg t.i.d. + 1.0 mg *1/4mg t.i.d.), or 4.5 mg (1.0 mg t.i.d. + 1.0mg*1/2 t.i.d.)

During the 7-week up-titration phase, the need for up-titration will be assessed by the investigator at on-site visits and telephone contacts, based on efficacy (PGI-I) and tolerability. Between on-site visits, the investigator will contact the patient by phone call to check efficacy (PGI-I) and tolerability of the study treatment and, if necessary, decide if the dose level has to be up-titrated or down-titrated. The dose of study medication should be up titrated in all patients who are not at least “a little better” on the PGI-I. If the dose is not increased, the reason should be given by the investigator and recorded in the eCRF (e.g. dose not increased due to an Adverse Event). In case of dopaminergic side effects (dyskinesia, psychosis, etc.) during the up-titration phase, the investigator can reduce the level of the study medication to the previous dose level.

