4.1.4 Drug assignment and administration of doses for each patient

The study consists of an 18-week, active treatment phase (up to a 7-week titration phase until optimal response, followed by an 11-week maintenance phase). At the end of the maintenance phase, patients who want to enter a down-titration phase, with a final visit to monitor tapering of the study medication. For other patients who want to maintain their

dosages, commercial Pramipexole IR/SR will be provided by themselves under the judgement of investigators.

Study site authorized personnel (registered in the investigator site file) will dispense the study medication during the on-site visits.

Pramipexole IR doses will be taken orally, in equally divided doses, three times per day with the third dose at 7-9 pm before bedtime, with a glass of water (approximately 150 mL) with or without food.

Pramipexole SR doses will be taken orally q.d. at 7-9 pm before bedtime. Each dose will be taken with a glass of water (approximately 150 mL) with or without food

Missed doses of IR will be skipped at any time.

Missed dose of SR should be taken within 12 hours after the regularly scheduled time. After 12 hours, the missed dose should be left out and the next dose should be taken on the following day at the next regularly scheduled time.

The dose level determined at the end of the titration phase will be maintained throughout the Maintenance Phase. Patients will use their last maintenance dose on the day of visit 7.

Patients who won't continue Pramipexole IR/SR treatment after trial completion will enter a down-titration phase on the day following Visit 7. Patients will take the taper medication during the week between visit 7 and follow-up visit 8. The medication dose will be reduced daily by one dose level. This tapering will take a maximum of six days (for patients treated with the highest dose level of 4.5 mg per day during the maintenance phase). Patients will return for a follow-up visit (visit 8) at last study dose + 2 days after visit 7 (at least 48 hours after the last study drug intake in the down titration phase).

Commercial Pramipexole IR/SR is allowed to be prescribed to patients at visit 7 in the judgement by investigators and patients. In this case, taper process is not applicable to those patients. However, all other procedures at visit 7 and visit 8 will be performed as no major changes, except for compliance check of taper medication.

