6.2.3 Follow up period and trial completion

Visit 8 - 2 days after the last study dose +3 days:

All assessments planned at this visit must be performed by all subjects after 48 hours of the last intake of study medication (+3 days), including those who have been prematurely withdrawn from the trial. Study medication should be completely tapered according to clinical practice at this visit except the patient who will continue the Pramipexole IR/SR treatment. Assessments performed during visit 8 include the following:

- Obtain vital signs (blood pressure, pulse) and weight
- Perform MMIDI interview
- Collect fasted blood sample for safety laboratory evaluation if abnormal at visit 7
- Perform 12-lead ECG if abnormal at visit 7

- Perform compliance check of taper medication
- Review concomitant therapies including PD therapies
- Record AEs or follow-up on AEs continuing from a prior visit

End of the trial is defined as the last visit (**follow up visit**) completed by each patient.

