7.3.4 Safety analyses

Adverse events will be coded using the Medical Dictionary for Drug Regulatory Activities (MedDRA). Standard BI summary tables and listings will be produced. All adverse events with an onset between start of treatment and end of the residual effect period (REP), a period of 2 days (inclusive) after the last dose of trial medication, will be assigned to the on-treatment period for evaluation.

All treated patients will be included in the safety analysis. In general, safety analyses will be descriptive in nature and will be based on BI standards. No hypothesis testing is planned.

Statistical analysis and reporting of adverse events will concentrate on treatment-emergent adverse events, i.e. all adverse events occurring between start of treatment and end of the

residual effect period. Adverse events that start before first drug intake and deteriorate under treatment will also be considered as ‘treatment-emergent’.

Frequency, severity, and causal relationship of adverse events will be tabulated by system organ class and preferred term after coding according to the current version of the MedDRA at the database lock.

Laboratory data, vital signs, physical examinations, or other safety-relevant data will be analysed quantitatively or qualitatively. MMIDI will be analysed descriptively. Details will be provided in the TSAP.

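### The Visit 7 instruction to book Visit 8 a week later contradicts the last-dose window at three of seven dose levels and for all patients who do not taper

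*Protocol*

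**What the plan says.** The last item in the Visit 7 list (protocol section 6.2.2.3) is "Schedule patient's next visit (Visit 8) one week later". It makes no exception for dose or taper, gives no tolerance and does not refer to the last dose. Section 4.1.4 also describes the taper as filling the week between Visits 7 and 8, so the one-week idea appears twice.

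Elsewhere Visit 8 is anchored to the last study dose:

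- Section 6.2.3 heads the visit "Visit 8 - 2 days after the last study dose +3 days" and adds "All assessments planned at this visit must be performed by all subjects after 48 hours of the last intake of study medication (+3 days".
- The flow chart column gives last study dose +2 days with a window of +3 days. Its footnote 2 says the visit "should be conducted after the end of residual effect period (i.e., 2 days after the last study dose".
- Section 4.1.4 asks for at least 48 hours after the last intake in the down-titration phase.

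Section 7.3.4 sets the residual effect period, to whose end treatment-emergent events are counted, at "a period of 2 days (inclusive) after the last dose of trial medication".

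**The concern.** A booking at a fixed interval from Visit 7 can agree with a window counted from the last dose only if the last dose falls at a suitable, fairly constant distance from Visit 7. Here that distance depends on the maintenance dose and on whether the patient tapers at all.

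Two consequences would follow.

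- **Adverse event collection.** Under section 5.2.6.2 all adverse events are collected until the individual patient's end of trial. After that, only related serious events that come to the investigator's notice are reported, and not in the CRF. Section 6.2.3 equates end of trial with the follow-up visit. A Visit 8 held too early would therefore close active collection inside the period that section 7.3.4 counts, and only for patients on the highest dose.
- **Deviations.** Sites that follow the Visit 7 line would incur window deviations caused by the protocol's own wording. The Visit 8 vital signs, MMIDI and any repeat laboratory test or ECG would be mistimed in the same way.

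**Working it through.** This is a day count, with Visit 7 as day 0.

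**Inputs**

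- Section 4.1.2: the doses "consist of the following seven dose levels", namely 0.375, 0.75, 1.5, 2.25, 3.0, 3.75 and 4.5 mg.
- Section 4.1.4: "Patients will use their last maintenance dose on the day of visit 7". The taper starts the next day and goes down one level per day.
- Section 4.1.4: patients moving to commercial product do not taper. Section 6.2.2.3 has them return their study medication at Visit 7, so their last study dose is no later than day 0.
- Flow chart and section 6.2.3: Visit 8 at last study dose +2 days, window +3 days.
- Section 7.3.4: residual effect period of 2 days after the last dose.

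**Formulas.** Number the levels k = 0 (0.375 mg) to k = 6 (4.5 mg). There are k lower levels, so the taper takes k days and the last study dose is on day k. The Visit 8 window is day k+2 to day k+5, and the residual effect period ends on day k+2.

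**Check against the protocol's own figure.** Section 4.1.4 states "This tapering will take a maximum of six days (for patients treated with the highest dose level of 4.5 mg per day". At 4.5 mg, k = 7 − 1 = 6 days, so the figure is reproduced.

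**Day 7 against each window**

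| Maintenance dose | Last study dose (day) | Residual effect period ends (day) | Visit 8 window (days) | Day 7 |
|---|---|---|---|---|
| No taper | 0 | 2 | 2–5 | 2 days late |
| 0.375 mg | 0 | 2 | 2–5 | 2 days late |
| 0.75 mg | 1 | 3 | 3–6 | 1 day late |
| 1.5 mg | 2 | 4 | 4–7 | inside, last day |
| 2.25 mg | 3 | 5 | 5–8 | inside |
| 3.0 mg | 4 | 6 | 6–9 | inside |
| 3.75 mg | 5 | 7 | 7–10 | inside, first day |
| 4.5 mg | 6 | 8 | 8–11 | 1 day early |

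Day 7 is inside only when k+2 ≤ 7 ≤ k+5, that is for k = 2 to 5. Three of the seven levels fail, as does every patient who does not taper.

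**Hours, under an added assumption.** Evening doses are taken at 7–9 pm. Suppose clinic visits run from 08:00 to 17:00 (my assumption; the protocol gives no clinic hours). The gap from last dose to a day-7 visit is then:

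- 4.5 mg: from 24 + 8 − 21 = 11 h to 24 + 17 − 19 = 22 h.
- 3.75 mg: from 48 + 8 − 21 = 35 h to 48 + 17 − 19 = 46 h.

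Read strictly in hours, the 48-hour requirement would also fail at 3.75 mg, making four of seven levels.

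**Would another fixed interval work?** A visit on day w fits levels with w−5 ≤ k ≤ w−2, which is at most four values of k. No single interval from Visit 7 satisfies all seven windows, so changing the one-week figure to another number cannot remove the conflict.

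**The case against.** The strongest reply is that the last-dose rule is stated several times, in mandatory terms, and that section 6.1 points to the flow chart for all visit windows. On that view the Visit 7 line is only a booking prompt, like those at Visits 5 and 6 for four and six weeks ahead, which also carry no tolerance. A site reading the whole protocol would apply the window, and section 6.1 sends out-of-window visits to the sponsor for discussion.

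This limits the harm but does not remove the contradiction. The prompts at Visits 5 and 6 fall exactly on the centre of their windows (week 8 to week 12, week 12 to week 18). The Visit 8 prompt does not, and section 4.1.4 reinforces it.

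The reply is right about size:

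- Only tapering patients at 4.5 mg would be seen before the residual effect period ends, and by one day.
- At 0.375 mg, at 0.75 mg and without a taper the visit would come after that period, so no countable event is lost. These are window deviations only.
- Patients on commercial product keep taking pramipexole, so a visit two days late has little bearing on their residual-effect safety.
- Persisting adverse events are followed up after the trial, safety analyses are descriptive, and the week-18 endpoint is collected at Visit 7.

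**Conclusion.** The text is wrong as written. The Visit 7 booking instruction cannot be reconciled with the Visit 8 window at 0.375, 0.75 and 4.5 mg, or for any patient who does not taper. At 4.5 mg it also places the visit before the residual effect period ends (day 7 against day 8). This is an internal contradiction with a small effect: about one day of active adverse event collection at the highest dose, and deviations of one to two days in the other affected groups.

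The result rests on counting in calendar days and on the taper running as section 4.1.4 describes. Counting in hours would add the 3.75 mg level. Patients who stop early may have taken their last dose before Visit 7, which would make a one-week booking later still. The protocol does not say how many patients will be at each level or will taper, so the number affected cannot be given.

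**What to change.** Reconcile the Visit 7 instruction in section 6.2.2.3, and the one-week wording in section 4.1.4, with the flow chart and section 6.2.3. One rule should determine Visit 8 for tapering and non-tapering patients alike, and active adverse event collection should span the residual effect period defined in section 7.3.4. No view is offered here on which schedule or taper is right; that is for the sponsor to settle.

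The cost is a line or so of wording at each place, with no extra visits, assessments or change to the analysis.
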